### 11. ETHICS

### Institutional Review Board (IRB)

Prior to participating in this investigation, the site will be required to obtain approval from its governing IRB. The Principal Investigator is responsible for obtaining and maintaining IRB approval to participate in this investigation. Prior to subject enrollment, a signed copy of the IRB approval letter addressed to the Investigator certifying study approval must be submitted to the Sponsor. The IRB for this study is the local IRB at Indiana University Hospital. The Investigator will report to the Sponsor immediately if, for any reason, the approval to conduct the investigation is withdrawn. This report will include a complete description of the reason(s) for which approval was withdrawn.

### **12. DATA MONITORING**

#### Data Review

The Sponsor will review all CRFs for completeness and clarity upon receipt. Missing or unclear data will be requested as necessary throughout the study. The Sponsor will request further documentation such as physician procedure notes when UADEs and/or malfunctions are observed and reported.

Protocol #: IU IRB# 1810997768 Date: 31AUG21 Page 14 of 17

The Sponsor will provide clinical monitoring including comparison of CRFs to source documentation for accuracy and appropriateness, review of/for adverse events, prompt evaluation of UADE, and site compliance. To this end, the Principal Investigator will permit inspection of the study files and subject CRFs by Sponsor representatives and/or responsible government agencies.

Prior to initiation of the study, sites will be trained on the clinical protocol, accepted clinical practices and Federal regulations pertaining to clinical research. Study sites will receive interim monitoring, as needed, and a final visit prior to study closure.

#### **Compliance and Deviations**

It is expected that sites (Investigators, study coordinators, ancillary site personnel, and study subjects) will be compliant with the study protocol. Should it be determined that the site is non-compliant, reasonable efforts will be made to secure compliance. These efforts/actions shall be documented in writing and maintained within the study administration file at the Sponsor's location.

Should the site continue to remain non-compliant, the study Sponsor may restrict device availability and/or notify the governing IRB. Should efforts to bring the site into compliance fail, the site may be suspended from study participation until the noncompliance is resolved. Federal regulations require the Sponsor to report non-compliances in the study to the appropriate regulatory authorities. Therefore, in the event of an Investigator or site suspension, the governing IRB and other appropriate regulatory authorities shall be notified.

#### **Protocol Deviations**

Protocol Deviations (PDs) will be documented on a Protocol Deviation Case Report Form. PDs are reportable to the institution's governing IRB and regulatory agencies during the annual reporting process, unless otherwise directed by the individual governing IRB requirements or as the specific circumstance dictates. Every attempt shall be made to adhere to the study protocol. However, should an Investigator be required to deviate from the protocol to protect the life or physical well-being of a study subject in an emergent circumstance, such notice shall be given to the study Sponsor as soon as possible, but no more than 5 working days from the date the event occurred. With the exception of an emergent circumstance, prior approval from Sponsor and the appropriate regulatory authorities is required for any change in, or deviation from, the study protocol as such changes may affect the soundness of the investigation or the rights, safety, and welfare of study subjects.

### **Data Safety Monitoring**

Two gastroenterologists ([name] and [name]), who are not a part of the study, will review adverse events, serious adverse and protocol deviations at the Indiana University site. These events and deviations will also be reported to the IU IRB as required. They will review all serious adverse events within 24 hours of their occurrence. Once 62 participants have been randomized, an interim analysis will be completed to review efficacy of primary endpoint, adverse events, serious adverse and protocol deviations. A final safety review will be performed once all the subjects complete the study.

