Follow-up Visits	Patient will complete a mail-in survey after 48 hours.
End of Study Visit	N/A
Brief Analysis Plan	Based on the literature the incidence of hypoxemia (ie: oxygen saturation < 90% for > 15 seconds) in using supplemental oxygen with nasal cannula is as high 43%. (Patel et. al.) Thus we expect the complication rate of hypoxemia in the SuperNO 2 VA™EtCO2 group to be 13%, we need 62 patients per group (112 patients in total) to detect this expected difference with 80% power at 0.05 two-sided level of significance. To adjust for 10% missing rate, we need approximately 124 patients in total.

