### An adverse event does not include:

- Medical or surgical procedures; the condition that leads to the procedure is not an adverse event
- Pre-existing disease, conditions, or laboratory abnormalities present at the start of the study that do not worsen in frequency or intensity
- Situations where an untoward medical occurrence has not occurred (e.g., hospitalizations for cosmetic or elective surgery or social/convenience admissions)
- Expected ICU course

Protocol #: IU IRB# 1810997768 Date: 31AUG21 Page 11 of 17

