### 7.3. Responsibilities for Reporting Serious Adverse Events

All adverse events, whether observed by the Investigator, elicited from or volunteered by the subject, should be documented. Each adverse event will include a brief description of the experience, the date of onset, the date of resolution, the duration and type of experience, the severity, the relationship to investigational product (i.e., drug or device), contributing factors, and any action taken with respect to the study drug/device.

Investigators and research coordinators will be instructed that all AE and corresponding relevant information should be recorded on the Adverse Event Form. In addition, the clinical site will be responsible for notifying Sponsor within 24 hours of any UADE. All relevant information regarding an UADE should be recorded on the Adverse Event Form and reported to Sponsor via Fax within 24 hours of the event. In addition to the event form, copies of adverse device effect related source documents should be forwarded to the Sponsor.

The Principal Investigator is responsible for reporting AEs to the IRB of record in accordance with IRB procedures. The Sponsor is responsible for informing the appropriate regulatory authorities and other Investigators of any UADEs that have occurred.

The Principal Investigator will record all serious adverse experiences that occur during the study period in the appropriate source documents and/or AE log as applicable.

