### 8. RISK/BENEFIT ASSESSMENT

### 8.1. Potential Risks

As with use of all medical devices, complications may occur. Recognized risks associated with the use of the study intervention include, but are not limited to, the following:

- Allergic reactions: although the materials being used are hypoallergenic and the risk is small, there remains a risk for an allergic reaction that may result in hives, swelling, or anaphylaxis.
- Ocular injury: although the SuperNO2VA Et™ Mask was designed to contour away from the eyes, mishandling of the mask or accidental slippage from its intended position may result in contact with the subject's eye, resulting in a corneal abrasion and/or other ocular injury.
- Pressure ulcer: although the clinical protocols states to remove the SuperNO2VA Et™ after successful placement of an invasive airway, if the SuperNO2VA Et™ is mistakenly left on the subject for an extended period of time it can lead to a pressure ulcer.

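### The 24-hour SAE review has no notification route to its reviewers, and its clock can expire before a post-discharge event is known; the listed questionnaire items do not ask about the named device harms

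*Protocol*

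**What the plan says.** **Review duty.** Protocol Section 12, Data Safety Monitoring, gives two gastroenterologists who are not part of the study the job of reviewing adverse events, SAEs and deviations. For SAEs it adds a deadline: "They will review all serious adverse events within 24 hours of their occurrence". The same paragraph plans a review once 62 participants have been randomized and a final safety review at the end.

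**Reporting duty.** Section 7.3 is headed as covering SAE reporting. Its only 24-hour duty is that "the clinical site will be responsible for notifying Sponsor within 24 hours of any UADE", with the form to be "reported to Sponsor via Fax within 24 hours of the event". For SAEs in general, the Principal Investigator "will record all serious adverse experiences that occur during the study period in the appropriate source documents and/or AE log as applicable". Section 7.3 also asks for every adverse event to be documented on the Adverse Event Form, whether observed, elicited or volunteered. Adverse events go to the IRB under that board's procedures, with no time given.

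**Contact after discharge.** The Summary Table (Follow-up Visits) says "Patient will complete a mail-in survey after 48 hours". Section 5.2 instead places the second questionnaire within 48 hours, on paper or by e-mail, and has non-responders telephoned at no stated time. It describes the content as satisfaction and perceived impairment from sedation.

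**Known device risks.** Section 8.1 names allergic reaction ("there remains a risk for an allergic reaction that may result in hives, swelling, or anaphylaxis"), ocular injury and pressure ulcer.

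**The concern.** The two reviewers are outside the study, so they learn of an SAE only if someone tells them. The protocol sets them a deadline but gives no one the matching duty to notify. The deadline also runs from the event itself, in an outpatient population that is seen once and then reached by a single questionnaire.

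The listed questionnaire content adds a second gap. If no item asks about eye, skin, allergic or breathing problems, harms that appear at home are recorded only when a patient raises them unprompted. A small number of reported device injuries could then reflect limited questioning as much as safety, and the halfway and final safety reviews would work from incomplete data.

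**Working it through.** The plan gives no numerical figure to reproduce here. The check compares the sections and adds a simple calculation of time lags.

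**1. Who is told, and when**

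| Event | Timed notice in Section 7.3 | Recipient | Stated route to the two reviewers |
|---|---|---|---|
| UADE | 24 hours | Sponsor | None |
| Any other SAE, device-related or not | None | Source documents and/or AE log; IRB under its own procedures | None |

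No class of SAE has a stated route to the reviewers, including UADEs. Section 12 sets their deadline but does not supply the route.

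**2. When a post-discharge SAE becomes known**

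Let *t* be the hour of the event and *C* the hour of contact, both counted from the procedure. If the questionnaire is the only source, the site learns of the event *C − t* hours after it occurred. Review within 24 hours of occurrence is possible only if *C − t* ≤ 24, that is, *t* ≥ *C* − 24. Events before hour *C* − 24 are already late when first known. The documents support a contact at about 48 hours; the other values of *C* are assumptions that show the range.

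| Contact hour *C* | Calculation | SAEs already late when known |
|---|---|---|
| 24 (assumed: early reply) | 24 − 24 = 0 | none |
| 36 (assumed) | 36 − 24 = 12 | 0 to 12 h |
| 48 | 48 − 24 = 24 | 0 to 24 h |
| 72 (assumed: postal delay or late call) | 72 − 24 = 48 | 0 to 48 h |
| 96 (assumed) | 96 − 24 = 72 | 0 to 72 h |

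This is a bound on awareness alone and leaves no time for the review itself when *t* is exactly *C* − 24. The result depends on *C*, and the documents do not fix *C*. The Summary Table implies 48 hours or later, Section 5.2 implies 48 hours or earlier, and the telephone call has no time. For an SAE seen in the suite or in recovery the detection lag is about zero, and only the missing route in step 1 matters.

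**3. What the patient is asked**

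The Summary Table lists 14 items for the 48-hour questionnaire (9a to 9n): overall experience, sedation quality, two on pain, nausea, vomiting, dizziness, two on recall of the scope, being awake, two on driving, one on working and one on time asleep. Against the harms:

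- Allergic reaction (Section 8.1): no item.
- Ocular injury (Section 8.1): no item.
- Pressure ulcer or facial skin injury (Section 8.1): no item. The redness check every 30 minutes in Section 8.2 applies only while the mask is on.
- Breathing trouble or unplanned medical care: no item.

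Section 7.3 accepts events elicited from the subject, but nothing described in the documents elicits these after discharge.

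**The case against.** The strongest reply is that the review rule can be met. Patients are monitored continuously in the suite and in recovery, where a serious reaction is most likely to be seen, and nothing prevents staff from telling the reviewers the same day. Patients can also telephone. This stands. A reader might infer that the rule cannot be met for listed device harms or for post-discharge events, and the documents do not support that. They show a deadline without a supporting route, and a clock that may expire in some cases. Even with contact at 48 hours, an SAE between 24 and 48 hours is learned in time.

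A reader might also infer that the gap arises because anaphylaxis and similar harms are listed in Section 8.1 and so escape the UADE notice. That does not explain it: the UADE notice goes to the Sponsor, so UADEs do not reach the reviewers by a stated route either. How a given event would be classified under Section 7.2 also depends on severity and on product information that is not part of these documents. Likewise, the exclusion of "Expected ICU course" from adverse events may look like a way to lose serious events. The protocol describes no planned ICU stay for these outpatients, so the text does not show that the exclusion has any effect.

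It is also fair that Section 7.3 does more than log SAEs. It requires the Adverse Event Form and IRB reporting, and Section 12 has the Sponsor review adverse events. None of these carries a time limit for a non-UADE SAE or sends it to the two reviewers.

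Finally, the Summary Table lists outcomes to be compared; the questionnaire and the Adverse Event Form themselves are not supplied and may contain more. Not every eye or skin injury would be serious, so the content gap concerns capture of harms in general as well as the SAE deadline.

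**Conclusion.** The point holds as a gap in safety oversight that is cheap to close. Three things are established from the text: the 24-hour review covers all SAEs and runs from occurrence; no SAE has a timed notice to the people who must review it; and the listed post-discharge items ask about none of the three harms named in Section 8.1, nor about breathing problems or unplanned care.

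The size of the timing problem depends on when contact happens. At 48 hours, SAEs in the first 24 hours after the procedure are late unless seen on site or volunteered. The affected window ranges from none (contact at 24 hours) to the first 72 hours (contact at 96 hours) under the assumed contact times. The conclusion assumes that the questionnaire is the only planned source after discharge and that its content is what the Summary Table and Section 5.2 describe. The primary analysis, sample size, power and alpha are untouched.

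**What to change.** 1. In Section 7.3 and Section 12 (Data Safety Monitoring), run the clock from the time the site becomes aware of the event. Have the site notify both the two reviewers and the Sponsor of every SAE within 24 hours of awareness, with UADEs as a subset of that flow.
2. Reconcile the questionnaire timing between the Summary Table and Section 5.2, and give the telephone back-up a time.
3. Add short yes/no items to the existing discharge and 48-hour questionnaires: eye symptoms; facial skin injury; rash or swelling; breathing problem or unplanned medical contact. Ask them in both arms, since Section 5.4 allows control patients to cross over to the mask and a comparison needs equal questioning. Enter any yes on the Adverse Event Form.

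The cost is amendment wording and a few questionnaire items. The questionnaires and the telephone back-up already exist. The downside is a few more minor adverse events to log.

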#### **Investigator Reports and Responsibilities**

Investigators are responsible for ensuring the investigation is conducted in accordance with the study protocol and applicable Federal regulations (21 CFR, Part 812, Subpart E).

Protocol #: IU IRB# 1810997768 Date: 31AUG21 Page 15 of 17

### Investigators are also responsible for:

- Obtaining IRB approval for study conduct and re-approval as applicable (if more than one Investigator is participating in the study at a site, the Principal Investigator shall be responsible for the IRB approval and re- approvals)
- Obtaining informed consent of study subjects prior to enrollment into the clinical study
- Protecting the subject rights, safety, and welfare
- Maintenance of subject records and confidentiality
- Record retention as defined in Federal regulations 21 CFR, Part 812.140 (a), (d), and (e)
- Management of investigation and study related activities according to the Clinical Investigator Agreement and the Study Research Agreement
- Submission of site-specific study closure report to governing IRB within 3 months of notification from study Sponsor (if more than one Investigator is conducting the study, the Primary Investigator is responsible for submission of the study closure report)
- Return of any unused investigational product to the study Sponsor upon request or at the conclusion of the clinical study

## In addition:

- An Investigator shall report to the Sponsor, within 5 working days, a withdrawal of approval by the reviewing IRB of the Investigator's part of an investigation
- If an Investigator uses a device without obtaining informed consent, the Investigator shall report such use to the Sponsor and the reviewing IRB within 5 working days after the use occurs
- An Investigator shall, upon request by a reviewing IRB or regulatory agency official, provide accurate, complete, and current information about any aspect of the investigation

### Sponsor Reports and Responsibilities

The study Sponsor is responsible for ensuring the study is conducted in accordance with the study protocol and applicable federal regulations (21 CFR, Part 812, Subpart C). Further, the study Sponsor is responsible for the following:

- Selecting qualified Investigators and providing Investigators with appropriate information for study conduct
- Ensuring review and approval process for governing IRB is obtained
- Training all clinical investigators in the study
- Appropriate monitoring of the clinical study
- Prompt notification to the appropriate regulatory and all Investigators of UADE
- Record maintenance and retention per Federal regulations (21 CFR, Part 812.140 (b), (d), and (e)
- Submission of final study closure report that details cumulative study experience to the appropriate regulatory authorities, governing IRBs, and Investigators within 6 months of completing the clinical investigation in addition to fulfilling annual reporting requirements

#### In addition:

• A Sponsor who conducts an evaluation of an UADE shall report the results of such evaluation to all reviewing IRBs and participating Investigators within 10 working days after the Sponsor first receives notice of the effect. Thereafter the Sponsor shall submit such additional reports concerning the effect as an IRB request

Protocol #: IU IRB# 1810997768 Date: 31AUG21 Page 16 of 17

- A Sponsor shall notify all reviewing IRBs and participating Investigators of any withdrawal of approval of an investigation or a part of an investigation by a reviewing IRB within 5 working days after receipt of the withdrawal of approval
- At regular intervals, and at least yearly, a Sponsor shall submit progress reports to all reviewing IRBs. In the case of a significant risk device, a Sponsor shall also submit progress reports to the regulatory authority
- A Sponsor shall notify all reviewing IRBs of any request that an Investigator return, repair, or otherwise dispose of any units of a device. Such notice shall occur within 30 working days after the request is made and shall state why the request was made
- In the case of a significant risk device, the Sponsor shall notify the IRB within 30 working days of the completion or termination of the investigation and shall submit a final report to all reviewing IRBs and participating Investigators within 6 months after completion or termination. In the case of a device that is not a significant risk device, the Sponsor shall submit a final report to all reviewing IRB's within 6 months after termination or completion
- A Sponsor shall submit to the IRB a copy of any report by an Investigator of use of a device without obtaining informed consent, within 5 working days of receipt of notice of such use
- If an IRB determines that a device is a significant risk device, and the Sponsor had proposed that the IRB consider the device not to be a significant risk device, the Sponsor shall submit to the appropriate regulatory agency a report of the IRB's determination within 5 working days after the Sponsor first learns of the IRB's determination
- A Sponsor shall, upon request by a reviewing IRB, provide accurate, complete, and current information about any aspect of the investigation

# **Study Termination**

The Sponsor may terminate the study at any time. If terminated, the Sponsor will promptly notify the Investigator to cease enrollment of subjects. The study will also be terminated when the objectives have been fully met and all of the designated data collected.

# **Study Registration**

The study will be listed at www.clinicaltrials.gov.

1. SAMPLE SIZE DETERMINATION AND DATA ANALYSIS

1.1. Sample Size Determination

Power analyses were performed for the three primary objectives, using a power level of 0.80 and an alpha level of 0.05. Based on the literature the incidence of hypoxemia (ie: oxygen saturation < 90% for > 15 seconds) in using supplemental oxygen with nasal cannula is as high 43%. (Patel et. al.) Thus we expect the complication rate of hypoxemia in the SuperNO₂VA Et^M group to be 13%, we need 62 patients per group (124 patients in total). This sample size will allow us to detect this expected difference with 80% power at 0.05 two sided level of significance. To adjust for 10% missing rate, we need approximately 124 patients in total.

1.2. Randomization

A random number generator program will be used to assign sequential qualified study cases to control group (N = 62) or SuperNO₂VATMEtCO2 group (N = 62) before collection of additional demographic information and before anesthetic and surgical care. After study group assignment, baseline data will be collected, including age, gender, height, weight, and BMI.

1.3. Planned Statistical Analysis

Although randomization into treatment groups should minimize differences between the groups, basic bivariate analyses will be performed to determine if there are any clinical or demographic differences, using the data collected in table 1. Logistic regression models will be performed to determine if there are significant differences between the groups for both incidence and severity. Student's t-tests will be performed to determine if there is a significant difference between groups for duration, with Wilcoxon non-parametric tests being performed if the data are non-linear. If significant differences in clinical or demographics characteristics were found, multivariable models will be performed to adjust for these possible confounding variables using logistic regression and ANCOVA models (with GEE models being used to model non-linear data with the appropriate exponential family distribution). All analytic assumptions will be verified and all analyses performed with SAS v9.4, SAS Institute, Cary, NC), analyzing the data as both per-protocol and intention-to-treat.

A Data Safety and Monitoring Board (DSMB) will be convened once half the necessary study population has been enrolled, to discuss the current status of primary endpoints and adverse events, all of which will be tabulated throughout the study. If effect sizes are larger than originally planned and there is a statistically significant decrease in the primary event at this halfway mark, the study will end at this time.

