### 5.4 Crossover to Other Group After Randomization

Patients in either Group A or Group B will be eligible for crossover to the other group at the discretion of the anesthesiologist in order to safely complete the procedure and minimize the likelihood of future adverse events.

Group A (Standard care with a nasal cannula) to Group B (SuperNO2VA™EtCO2) group will occur when during the procedure either: 1) twoor more simultaneous or non-synchronous adverse events related to changes in SBP, SpO2 or HR that do not respond to typical maneuvers to reverse these or; 2) any of the following two occur: a) any change in heart rhythm other than sinus bradycardia or sinus tachycardia or; b) ST changes appear on EKG occur.

Group B to Group A: If any of the following occur: 1) patient refusal to wear the mask once placed due to claustrophobia, poor fit or discomfort or any other reason; 2) two or more simultaneous or non-synchronous adverse events related to changes in SBP, Sp02 or HR that do not respond to typical maneuvers to reverse these or; 3) any of the following two occur: a) any change in heart rhythm other than sinus bradycardia or sinus tachycardia or; b) ST changes appear on EKG occur.

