#### **10.3.** Planned Statistical Analysis

Although randomization into treatment groups should minimize differences between the groups, basic bivariate analyses will be performed to determine if there are any clinical or demographic differences, using the data collected in table 1. Logistic regression models will be performed to determine if there are significant differences between the groups for both incidence and severity. Student's t-tests will be performed to determine if there is a significant difference between groups for duration, with Wilcoxon non-parametric tests being performed if the data are non-linear. If significant differences in clinical or demographics characteristics were found, multivariable models will be performed to adjust for these possible confounding variables using logistic regression and ANCOVA models (with GEE models being used to model non-linear data with the appropriate exponential family distribution). All analytic assumptions will be verified and all analyses performed with SAS v9.4, SAS Institute, Cary, NC), analyzing the data as both per-protocol and intention-to-treat.

A Data Safety and Monitoring Board (DSMB) will be convened once half the necessary study population has been enrolled, to discuss the current status of primary endpoints and adverse events, all of which will be tabulated throughout the study. If effect sizes are larger than originally planned and there is a statistically significant decrease in the primary event at this halfway mark, the study will end at this time.

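### Protocol 10.3 and SAP 1.3 do not say which result for desaturation incidence decides: adjustment depends on baseline significance tests, and intention-to-treat and an undefined per-protocol set are left unranked

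*SAP*

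**What the plan says.** Protocol 10.3 and SAP 1.3 carry the same text. Logistic regression is named for incidence and severity. For duration, "Student's t-tests will be performed to determine if there is a significant difference between groups for duration, with Wilcoxon non-parametric tests" are named, the second as a fallback.

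- **Adjustment.** First, "basic bivariate analyses will be performed to determine if there are any clinical or demographic differences, using the data collected in table 1". Then: "If significant differences in clinical or demographics characteristics were found, multivariable models will be performed to adjust for these possible confounding variables". No significance level is given for the baseline tests, no covariate is fixed in advance, and nothing says whether the unadjusted or the adjusted result is the main one.
- **Analysis sets.** The plan ends with "analyzing the data as both per-protocol and intention-to-treat". Neither document ranks the two or defines the per-protocol set.
- **Other methods.** Protocol 5.2 lists the t-test and Fisher's exact test and leaves further methods to the statistician's judgement.
- **Crossover.** Protocol 5.4: "Patients in either Group A or Group B will be eligible for crossover to the other group at the discretion of the anesthesiologist". In both directions one trigger is two or more "adverse events related to changes in SBP, Sp02 or HR that do not respond to typical maneuvers to reverse these". Rhythm or ST changes are a further trigger in both directions. Mask refusal is a trigger in Group B only. Neither document says how crossed-over patients are analysed.
- **Halfway look.** Protocol section 12, Data Safety Monitoring: "Once 62 participants have been randomized, an interim analysis will be completed to review efficacy of primary endpoint". SAP 1.3 ends the trial there on this condition: "If effect sizes are larger than originally planned and there is a statistically significant decrease in the primary event at this halfway mark". No analysis set or model is named for it.

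**The concern.** For incidence the plan can produce four results: ITT or per-protocol, each unadjusted or adjusted. Protocol 5.2 adds Fisher's exact test and an open choice beyond it. When the results differ, no rule says which one counts, either at the end or at a halfway look that can stop the trial.

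Two features make this more than a drafting gap. Whether an adjusted model is fitted, and on which covariates, depends on chance imbalances rather than on prognostic importance. And because low SpO2 is both the primary outcome and one of the crossover triggers, excluding crossed-over patients would partly select on the outcome.

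**Working it through.** **Inputs from the documents.** 43% vs 13%, two-sided 0.05, 62 per arm, 10% missing (Protocol 10.1, SAP 1.1). Table 1 (Protocol 5.2) has nine named rows plus a co-morbidity row listing 11 conditions. The documents give no crossover shares and no prognostic strength, so these are assumed below.

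**1. The plan's own figure.** With 62 per arm, 43% vs 13% has 97.3% power (exact, likelihood-ratio test) or 95.6% (Fisher). With 56 per arm, about 10% fewer, it is 95.7% or 93.4%. The stated 80% is therefore not reproduced. That is a separate matter; what counts here is that a single ITT comparison of incidence is well powered and needs no more patients.

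**2. How often the adjustment trigger fires by chance.** With k independent tests at an assumed 0.05 level, P(at least one significant) = 1 − 0.95^k.
- k = 9: 37%
- k = 10: 40%
- k = 20 (9 + 11): 64%

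Correlated rows, such as height, weight and BMI, lower these figures.

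**3. What the covariate rule does by itself.** Simulation with 62 per arm, 8,000 trials per setting, two prognostic covariates with a combined log odds ratio per SD of 0.2 to 1.0 (assumed), and eight noise rows. Rejection rates:

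| Setting | Log-OR per SD | Unadjusted | Conditional rule | Always adjusted |
|---|---|---|---|---|
| No difference, 43% in both arms | 0.2 | 5.6% | 5.2% | 5.2% |
| No difference, 43% in both arms | 1.0 | 5.4% | 4.8% | 5.3% |
| 43% vs 13% | 0.2 | 97.0% | 96.8% | 97.1% |
| 43% vs 13% | 0.4 | 97.1% | 97.0% | 97.2% |
| 43% vs 13% | 0.7 | 97.3% | 97.1% | 98.2% |
| 43% vs 13% | 1.0 | 97.1% | 97.2% | 98.6% |

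There is no inflation from the rule. Always adjusting gains about 0 to 1.5 points at the planned rates.

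**4. What dropping event patients does.** If a share c of event patients is excluded, an event rate p becomes p(1 − c)/(1 − pc). With 43% in both arms:
- c = 0.10: 0.387/0.957 = 40.4%
- c = 0.25: 0.3225/0.8925 = 36.1%

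Unequal shares thus create a difference of 4.3 points where none exists. Swapping the shares between arms reverses its sign.

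**5. Choice among four results with no true difference.** 62 per arm, 43% in both arms, 5,000 trials per setting, log odds ratio 0.2 and 1.0:

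| Event patients dropped (assumed) | At least one of four significant |
|---|---|
| None | 6.2%, 7.0% |
| 10% in both arms | 6.8%, 7.1% |
| 25% in both arms | 7.7%, 8.4% |
| 10% in one arm, 25% in the other | 10.1-11.8% |

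One fixed adjusted ITT model gave 4.9-6.0% in the same runs. A fresh simulation with the same structure gave 6.0-6.3%, 7.0-7.4%, 7.7-7.8% and 10.1-10.2% for the four rows, and 4.5-5.6% for the fixed model.

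**6. Events available for adjustment.** Expected events at the planned rates run from 56 × (0.43 + 0.13) = 31 to 62 × 0.56 = 35.

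**The case against.** The strongest reply is that the harm is small. The covariate rule leaves type I error alone, the power gain at the planned rates is at most about 1.5 points on 97%, and a fixed unadjusted ITT model would also give one deciding result. All of this stands. Choosing BMI and OSA as covariates is a cheap improvement; having one named result is the necessary part. The 10-12% figure needs assumed unequal dropping and a reader willing to claim any of the four results.

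Three stronger readings are tempting, and the documents do not support them.

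- A reader might infer that the per-protocol analysis would favour the mask. The direction cannot be stated: crossover is allowed both ways, no frequencies are given, mask refusal removes patients from one arm only, and the per-protocol set is undefined, so it may not exclude these patients at all.
- A reader might infer that any desaturation leads to crossover. Protocol 5.4 asks for two or more SBP, SpO2 or HR events that do not respond to the usual maneuvers, or one of the other listed triggers.
- A reader might infer that the halfway look stops at its nominal error rate. The rule needs a significant decrease and an effect above the planned one. With 31 per arm and 43% in both, an exact likelihood-ratio calculation gives 5.4% two-sided, 2.7% for a decrease, and 0.7% when the difference must also exceed 30 points (0.2% if the odds ratio must exceed 5.05). At 43% vs 13%, stopping falls from 78.5% to about 48-53%.

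The last point shows that the effect scale at the halfway look also has to be stated, all the more if the deciding model is adjusted, because an adjusted odds ratio is not on the same scale as the planned 43% vs 13%.

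**Conclusion.** The point holds as a gap in specification that should be closed. No passage says whether the ITT or the per-protocol result, unadjusted or adjusted, decides for incidence. The baseline-test trigger makes the adjusted model largely a matter of chance, and the undefined per-protocol set may select on the primary outcome.

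The size is modest: about 6-8% false-positive opportunity with no or equal dropping, and 10-12% under the assumed 10% and 25% shares, against 5-6% for one fixed ITT model. These figures rest on assumed dropping shares and prognostic strength, and on counting any of the four results as success. They describe the room for choice that the plan leaves, not a predicted error rate.

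The ranking of incidence, duration and severity, the methods for duration and severity, and the significance level at the halfway look are separate matters.

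**What to change.** In Protocol 10.3 and SAP 1.3, state:

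> The deciding analysis of desaturation incidence is ITT: all randomised patients with outcome data, in their assigned group, events counted regardless of crossover, by logistic regression on group, BMI and documented OSA, fitted whatever the baseline comparisons show. The unadjusted ITT result and the per-protocol result are supportive only. The per-protocol set is [definition fixed before analysis, stating how crossed-over patients are handled].

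Also:
- Delete baseline significance as the trigger for adjustment; Table 1 stays descriptive.
- Make the methods sentence in Protocol 5.2 refer to 10.3.
- State that the halfway efficacy look uses the ITT set, and that its condition on the size of the effect is judged on the unadjusted rates against the planned 43% vs 13%.

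The crossover rule in 5.4 is unchanged.

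Cost: a few sentences and no new data, since BMI and diagnosed OSA are eligibility factors already recorded in Table 1. The downside is two extra parameters on about 31-35 expected events. If the sponsor prefers not to carry them, a fixed unadjusted ITT model would also give one deciding result, without the small gain in power.
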